2.1 EVIDENCE

2.1.1 Serum neurotensin/IL-8 values in colorectal cancer

Serum neurotensin/IL-8 values in the diagnosis of colorectal cancer have been reported for first time in literature by our own group.[18, 19] This pilot study aimed to determine the feasibility of serum neurotensin/IL-8 values being used as a screening tool for colorectal cancer. Fifty-six patients and 15 healthy controls were assigned to seven groups according to their disease entity based on theater records and histology report. Blood samples for neurotensin and IL-8 were measured using an enzyme-linked immunosorbent assay.

There were no differences in the clinical and biochemical parameters of patients and controls. Group (p= 0.003) and age (p= 0.059: marginally significant) were independent predictors of neurotensin plasma values. Neurotensin (p= 0.004) and IL-8 (p= 0.029) differed between healthy and colorectal cancer patients. Neurotensin values differentiated the control group from all remaining groups.

The value of plasma neurotensin ≤54.47 pg/ml at enrollment selected by ROC curves demonstrated a sensitivity of 77%, specificity of 90%, and an estimate of area under ROC curve (accuracy) of 85% in predicting colorectal cancer.

At enrollment, the value of plasma IL-8 ≥8.83 pg/ml had a sensitivity of 85%, specificity 80%, and an estimate of area under ROC curve (accuracy) of 81% in predicting colorectal cancer.

Our results depicted that IL-8 should be used complementary to neurotensin due to its lower specificity. None of the colorectal cancer patients displayed a combination of high neurotensin and low IL-8 values (beyond cutoffs). Unpredictably, 3 out of 13 patients in the colorectal cancer group had neurotensin values above the cut-off value defined by the ROC curve. Notwithstanding, the IL-8 values of the same patients were high and well above the cut-off value, as our analysis anticipated for this group. Two other colorectal cancer group patients unexpectedly had low IL-8 values, but they also had low neurotensin values, as our analysis expected for this group. None of the colorectal cancer group patients displayed a combination of high neurotensin and low IL-8 values (which would be in contrast with our analysis).

Finally, one healthy control had a low neurotensin value as well as a low IL-8 value.

This pilot study[18] implicated that a blood neurotensin/IL-8 system may be used as a screening tool for colorectal cancer.

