Maoret et al [14] found that NT stimulated growth of five different human cancer lines (SW480, SW620, HT29, HCT116, C1.19A) shown to express NTSR1, whereas it had no effect on caco-2 cells shown to lack NTSR1. In SW480 cells, NT enhanced proliferation by two- to three-fold and increased colony formation by approximately 50%.

Gui et al [15] showed that NTSR1 expression enhancement is gradual through neoplastic transformation of colonic epithelium. In the normal colon, NTSR1 expression was principally confined to basal cells in the deep portion of the crypts, a compartment known to include the self-renewing epithelial stem cell population.[27] Quite the opposite, NTSR1 expression was weak to absent in superficial epithelial cells, suggesting that NTSR1 may be a factor in

supporting the growth of self-renewing cells, and that downregulation of the receptor may be necessary during terminal differentiation in the normal colonic epithelium. In addition, NTSR1 expression was generally higher in the deep advancing margins and invasion sites than in the rest of the tumor. Souaze et al [28] claim that the upregulation of NTSR1 in colon cancer is mainly assigned to activation of the Wnt/APC signaling pathway. Modifications in Wnt/APC take place frequently at the early premalignant stage, and are seen as critical to the progression of colon cancer. Activation of the NTSR1 gene was achieved by agents that triggered b-catenin buildup, as well as a drop in endogenous NTSR1 when the tumor suppressor gene APC was restored to cancer cells.

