3.1 CONTROL(S) / COMPARATOR(S)

All individuals fulfilling the inclusion criteria will be enrolled. After the refinement of participants by the exclusion criteria blood sample will be drawn for Neurotensin and IL-8. Following the report of colonoscopy and the histology individuals will be assigned in three groups: a) group A - cancer patients, b) group B – adenoma (polyp) patients and c) group C – No pathology/normal colonoscopy. Two primary analyses will be conducted to define the cut-off plasma values for Neurotensin and IL-8 for a) diagnosing cancer (group A versus group C) and b) diagnosing adenomas (group B versus group C). A secondary analysis will be conducted comparing the performance of the Neurotensin/IL-8 system towards the 2-weeks referral and FOB test positive patients for the diagnosis of colorectal cancer and adenomas.

The reason for using participants without bowel pathology is because we need to define the "normal range" of Neurotensin and IL-8 serum values.

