3.5 PROPOSED SAMPLE SIZE / POWER CALCULATIONS

Assuming that the AUC of the new test is commensurate with the pilot study (AUC=0.85), we calculate the number of samples required to obtain a 95%

confidence interval of size 0.1. We assume that the ROC curve follows a binormal distribution, and that the prevalence of adenoma/cancer is between 20-30% in the study participants. We obtain that we require between 400 (30% prevalence) and 553 (20% prevalence) participants. We therefore target an enrollment of 500 patients. We intend to perform an interim analysis after 50% of the patients have been included and evaluated.

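### The 0.1 confidence interval width in section 3.5 comes from a pooled adenoma/cancer case group and a cancer-only pilot AUC of 0.85, so it is not the expected width of either primary analysis

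*Protocol*

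**What the plan says.** Section 3.5 (sample size) plans for precision, starting from "Assuming that the AUC of the new test is commensurate with the pilot study (AUC=0.85". It assumes a binormal ROC curve, a 95% interval of total width 0.1, and a prevalence of adenoma and cancer taken together of 20-30%. From these it derives 400 participants (30%) to 553 (20%) and sets the target at 500.

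The pilot is described in section 2.1.1: "Fifty-six patients and 15 healthy controls were assigned to seven groups". For neurotensin it reports an "estimate of area under ROC curve (accuracy) of 85% in predicting colorectal cancer", and for IL-8 an "estimate of area under ROC curve (accuracy) of 81% in predicting colorectal cancer". The cancer group had 13 patients ("3 out of 13 patients in the colorectal cancer group had neurotensin values above the cut-off"). No AUC for adenomas appears anywhere in the protocol.

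Section 3.1 sets up two primary analyses. One compares cancer with normal (group A versus C); the other is "b) diagnosing adenomas (group B versus group C". Section 3.3 makes the AUC a primary endpoint for both conditions.

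**The concern.** The 0.85 is a figure for cancer, but section 3.5 applies it to a case group that also contains adenomas. That case group is pooled, whereas neither primary analysis uses pooled cases: each takes only its own cases against the normal group. The 0.1 is therefore the width for a comparison that is not among the primary analyses.

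Two consequences follow. Each primary analysis has fewer cases than the calculation counts. And if the markers separate adenomas from normals less well than they separate cancers, the variance of the adenoma AUC is larger than planned. A reader of section 3.5 would expect a precision of 0.1 for both primary AUCs, and the documents do not support that.

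**Working it through.** **Inputs.** From section 3.5: AUC 0.85, width 0.1 (half-width 0.05), prevalence 20-30%, N=500. From section 1.8: a cancer yield of 4% at colonoscopy, *assumed* here to hold in this cohort. Adenoma AUCs of 0.65 to 0.85 are *assumed*, because the protocol gives none. Every participant is taken to fall in group A, B or C.

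**Formula** (Obuchowski's binormal variance approximation), with n1 cases, n0 controls and R = n0/n1:

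- a = 1.414 × z(AUC)
- V = 0.0099 × exp(−a²/2) × [(5a² + 8) + (a² + 8)/R]
- width = 2 × 1.96 × √(V/n1)
- for a half-width of 0.05, n1 = 1.96² × V/0.05² and N = n1/prevalence

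**Step 1: the protocol's figures.** At AUC 0.85, a = 1.4655 and a² = 2.1477, so 0.0099 × exp(−a²/2) = 0.0033827.

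- 20%: R = 4; V = 0.0033827 × (18.7387 + 10.1477/4) = 0.07197; n1 = 110.6; N = 552.9.
- 30%: R = 2.333; V = 0.0033827 × (18.7387 + 10.1477/2.333) = 0.07810; n1 = 120.0; N = 400.0.

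Both stated figures reproduce, so this is evidently the protocol's method. At N=500 the pooled width is 0.1052 (20%) or 0.0894 (30%).

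**Step 2: split the cases.** 4% of 500 is 20 cancers. At 20% prevalence, 100 − 20 = 80 adenomas face 400 normals. At 30%, 150 − 20 = 130 adenomas face 350 normals. On this assumption adenomas make up 80% (80/100) to 87% (130/150) of cases.

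**Step 3: adenoma-versus-normal width at N=500.**

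| Adenoma AUC (assumed) | 20%: 80 v 400 | 25%: 105 v 375 | 30%: 130 v 350 |
|---|---|---|---|
| 0.85 | 0.1162 | 0.1034 | 0.0949 |
| 0.80 | 0.1261 | 0.1124 | 0.1035 |
| 0.75 | 0.1315 | 0.1176 | 0.1085 |
| 0.70 | 0.1342 | 0.1203 | 0.1113 |
| 0.65 | 0.1352 | 0.1214 | 0.1126 |

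Example, first cell: R = 5, V = 0.07025, width = 3.92 × √(0.07025/80) = 0.1162.

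**Step 4: where the widening comes from.** At 20% prevalence:

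- 553 pooled participants give 0.1000.
- Choosing 500 gives 0.1052 (+0.0052).
- Removing the cancers from the case count gives 0.1162 (+0.0110).
- Lowering the AUC to 0.75 gives 0.1315 (+0.0153), or to 0.65 gives 0.1352 (+0.0190).

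At 20%, then, 0.0162 of a total excess of 0.0315 to 0.0352 arises before any change of AUC. At 30%, 500 exceeds the 400 needed, so the pooled width starts at 0.0894. Splitting brings it to 0.0949, and only an AUC below 0.85 takes it past 0.1.

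**Step 5: cancer versus normal.** With 20 cancers at AUC 0.85 and 400 or 350 normals, V = 0.0651 or 0.0653 and the width is 0.2237 or 0.2241, about 0.22.

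**The case against.** The calculation is correct on its stated inputs, and 0.85 is openly labelled an assumption in a study that section 2 calls a pilot. No decision rule in the protocol depends on the width. Under the assumed AUCs of 0.65-0.75 the half-width moves only from 0.05 to between 0.054 and 0.068. At AUC 0.85 and 30% prevalence the adenoma width is 0.0949, inside the target even after the split. Other variance formulas also give different answers. At AUC 0.70-0.75 a binormal delta method gives 0.096-0.122 and Hanley-McNeil 0.106-0.136, though neither reproduces 400 and 553 (they give 252/331 and 338/484). All of this stands, and it makes the point one of restating precision, not of an error in N.

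A reader might infer more than the documents support:

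- *That the adenoma interval will be 0.11-0.135 wide.* That range needs an adenoma AUC of about 0.65-0.75, which no section supplies. It is not a floor for lower AUCs either: AUC 0.80 at 30% gives 0.1035.
- *That the protocol itself shows a weaker adenoma signal.* Section 2.1.2 reports that "NTSR1 expression enhancement is gradual through neoplastic transformation of colonic epithelium", but this concerns a receptor in tissue, whereas the test is serum neurotensin and IL-8. Section 2.1.4 leaves the relation between tissue expression and circulating level to future study. Section 2 also reports the receptor raised in adenomas as well as in cancers.
- *That 0.85 is cancer against healthy controls.* Section 2.1.1 does not name the ROC comparator, and the stated specificity of 90% is not attainable from 15 controls alone (13/15 = 87%, 14/15 = 93%). The point needs only that the figure is for predicting cancer.
- *That the protocol plans for mostly adenomas.* It gives no split. The 80-87% follows from a background remark in section 1.8 about current colonoscopy practice, which may not carry over to this cohort.

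**Conclusion.** The point holds as a gap between the precision stated and the analyses planned. Section 3.5 uses one pooled case group and one cancer-only AUC to justify a width of 0.1, while sections 3.1 and 3.3 call for two separate AUCs, one of them for a condition with no AUC in the protocol.

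If 4% of participants have cancer, the adenoma width at N=500 runs from 0.0949 to 0.1352 over AUC 0.65-0.85 and prevalence 20-30%. It exceeds 0.1 in every cell of the table except AUC 0.85 at 30%. The adenoma AUC range is an assumption, and at 20% prevalence about half of the excess has nothing to do with it. The larger shortfall is in the cancer analysis, at about 0.22, so a correction confined to adenomas would wrongly suggest that 0.1 holds for cancer.

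**What to change.** In section 3.5:

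1. State that 0.85 is the pilot's neurotensin AUC for colorectal cancer, that no adenoma AUC is available, and that the 0.1 width refers to adenoma and cancer cases pooled.
2. Replace the single 0.1 with the expected width of each primary analysis at N=500: adenoma versus normal about 0.095-0.135 over AUC 0.65-0.85 and prevalence 20-30%; cancer versus normal about 0.22 with about 20 cancers at AUC 0.85.
3. Label the AUC range and the 4% cancer share as assumptions.

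This takes a few sentences and a small table. N=500 is unchanged and no extra patients are needed. The cost is a less favourable stated precision, most visibly for cancer.

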1.8 THE NEED FOR A TRIAL

Colorectal cancer mortality can be lowered by both early diagnosis and cancer prevention.[1, 2] The objective of screening is to detect cancer at an early, curable stage. Individuals at average risk, those older than 50 years of age, with a negative family history and negative history of adenoma, colorectal cancer, or inflammatory bowel disease are among the highest yield group.

Recent literature proposes that after an initial negative colonoscopy (which is the current standard of screening not only in average risk but also in increased risk patients, should start at age 50 or earlier age with frequency depending on risk factors: e.g. personal/family history of polyps/cancer, inflammatory bowel disease, known genetic syndrome and prior colonoscopy findings), follow-up with rescreening after the age of 60 with annual guaiac fecal occult blood testing, annual fecal immunochemical testing, or computed tomographic colonography every five years provides approximately the same benefit in life-years with fewer complications and at a lower cost.[3] There is a lack of consensus concerning the use of CT colonography as a primary screening tool.

The number of CRC cases from colorectal cancer screening is still rather low. Sensitivity of guaiac tests for the detection of CRC/adenomas is 21.8%-46.3%.(4) Colonoscopy is the favoured screening method for individuals at average risk despite lower patient compliance with this modality. A meta-analysis of 14 randomized controlled trials documented that although endoscopic surveillance was superior to stool testing in detecting advanced neoplasms, its benefit was eclipsed by a lower participation rate.[4] Colonoscopy is the favored screening method for individuals at average risk despite lower patient compliance with this modality. Whilst colonoscopy is an outstanding tool for diagnosing potentially curable bowel cancer, too many patients are currently having an unnecessary procedure as the pick-up rate for bowel cancer is only 4%. Nevertheless, NCCN guideline panelists agree that any form of screening is better than none.[5]

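### Section 3.5 sizes the study on a pooled adenoma/cancer group, so its 95% CI width of 0.1 does not apply to the separate primary analysis of cancer versus normal

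*Protocol*

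**What the plan says.** Section 3.5 contains one sample-size calculation. It begins "Assuming that the AUC of the new test is commensurate with the pilot study (AUC=0.85" and continues "we calculate the number of samples required to obtain a 95" per cent "confidence interval of size 0.1". It takes a binormal ROC curve and assumes that "the prevalence of adenoma/cancer is between 20-30% in the study participants". The result is 400 participants at 30% prevalence and 553 at 20%, hence the target of 500.

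Section 3.1 defines three groups from colonoscopy and histology (A cancer, B adenoma, C normal) and names two primary analyses: "diagnosing cancer (group A versus group C) and b) diagnosing adenomas (group B versus group C"). Section 3.3 makes the AUC for predicting cancer and for predicting adenomas part of the primary endpoint, for both neurotensin and IL-8.

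Section 2.1.1 shows where the 0.85 comes from. For neurotensin the pilot found "an estimate of area under ROC curve (accuracy) of 85% in predicting colorectal cancer". For IL-8 it found "an estimate of area under ROC curve (accuracy) of 81% in predicting colorectal cancer". No pilot AUC for adenoma is reported.

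Section 1.8, in a general remark on current colonoscopy practice, says that "the pick-up rate for bowel cancer is only 4"%.

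**The concern.** The contrast that is sized, A and B together, is not among the planned primary analyses, and neither planned contrast has its own calculation. The pooled case group is large (100 to 150 of 500), and the number of cases is what mainly drives the precision of an AUC here. If cancers are a small part of that group, the cancer AUC will be estimated much less precisely than section 3.5 leads a reader to expect. The AUC input adds to the mismatch: it is the pilot's neurotensin AUC for cancer, paired with a prevalence that includes adenomas.

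Cancer is the first-listed primary analysis. A reader of section 3.5 would expect an observed cancer AUC of 0.85 to come with an interval of about 0.80 to 0.90. Section 5.5 makes a multicentre study depend on promising results, so the real precision should be known beforehand.

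**Working it through.** **Inputs.** AUC 0.85, 95% confidence, full width 0.1 (half-width 0.05), pooled prevalence 20% and 30%, n = 500 (all section 3.5); IL-8 AUC 0.81 (section 2.1.1); cancer pick-up 4% (section 1.8, background only). The 10% and 15% cancer yields are assumptions made here to show a range.

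**Step 1: reproduce the plan's figures.** The protocol names the binormal model but not the variance formula. The Obuchowski binormal approximation reproduces its numbers:

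V = 0.0099 × exp(−A²/2) × [(5A² + 8) + (A² + 8)/R], with A = 1.414 × probit(AUC), R = controls per case, and cases = 1.96² × V / 0.05².

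For AUC 0.85: A = 1.4655, A² = 2.148, exp(−A²/2) = 0.3417, 5A² + 8 = 18.739, A² + 8 = 10.148.

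- 20% (R = 4): V = 0.0099 × 0.3417 × (18.739 + 2.537) = 0.0720; cases = 110.6; total = 110.6/0.20 = 552.9. Stated: 553.
- 30% (R = 2.333): V = 0.0099 × 0.3417 × (18.739 + 4.349) = 0.0781; cases = 120.0; total = 120.0/0.30 = 400.0. Stated: 400.

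The Hanley-McNeil variance gives 484 and 338, so it is not the formula used. At n = 500 the pooled width is 0.105 (20%) to 0.089 (30%).

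**Step 2: cancer versus normal (A versus C) at n = 500.** Width = 2 × 1.96 × √(V / cases). At 4%, 500 × 0.04 = 20 cancers. With 350 normals, R = 17.5, V = 0.0653, and the width is 3.92 × √(0.0653/20) = 0.224. With 400 normals it is also 0.224, so the number of controls hardly matters.

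Two other variances serve as checks: Hanley-McNeil, and the exact variance of the empirical AUC for equal-variance binormal data.

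| Cancers (share of 500) | Controls | Formula matching 400/553 | Hanley-McNeil | Exact equal-variance |
|---|---|---|---|---|
| 20 (4%) | 350 | 0.224 | 0.214 | 0.169 |
| 30 (6%) | 350 | 0.184 | 0.176 | 0.140 |
| 40 (8%) | 350 | 0.161 | 0.153 | 0.123 |
| 50 (10%) | 350 | 0.145 | 0.137 | 0.111 |
| 75 (15%) | 425 | 0.119 | 0.112 | 0.092 |

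At 20 cancers an observed 0.85 would carry about 0.74 to 0.96 by the first method (0.85 ± 0.112) and about 0.77 to 0.93 by the last (0.85 ± 0.085). Within 500 participants, the first method needs about 113 cancers (22.6%) for a width of 0.1.

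**Step 3: adenoma versus normal (B versus C).** If the pooled 100 to 150 cases include 20 cancers, there are 80 to 130 adenomas and 400 to 350 participants without either. At AUC 0.85 the widths are 0.116 (80 versus 400) and 0.095 (130 versus 350). If cancers were instead 50, adenomas would be 50 to 100 and the widths 0.144 (50 versus 400) to 0.106 (100 versus 350: V = 0.0099 × 0.3417 × (18.739 + 10.148/3.5) = 0.0732; 3.92 × √(0.0732/100)).

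**Step 4: IL-8 at its own pilot AUC of 0.81.** A² = 1.541. The pooled requirement becomes 464.5 (30%) to 636.8 (20%), and the pooled width at n = 500 is 0.096 to 0.113. For 20 cancers and 350 normals it is 0.239.

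**The case against.** The strongest objection concerns the 4%. It describes colonoscopy in general and is not a projection for this cohort. Section 3.2.1 admits referrals under any indication but also lists bowel-habit change, rectal bleeding and positive FIT/FOB tests, so the yield may differ. This stands: 20 cancers is an illustration from the only figure in the document, not a prediction. The conclusion survives a wide range of yields. Up to 10%, all three methods miss 0.1. At 15% two still miss it and the exact equal-variance method gives 0.092. The protocol sets no minimum number of cancers.

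A reader might infer that the cancer interval will be more than twice the stated width. That depends on both the 4% and the formula: the exact equal-variance method gives 0.169, about 1.7 times the target.

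A reader might also infer that the study could not tell a useful marker from a poor one. The documents do not support that. Even 0.74 to 0.96 excludes chance, section 2 calls this a pilot of feasibility, and the earlier pilot had 13 cancer patients and 15 healthy controls. But section 3.5 still makes a specific precision claim, and pilot status does not make it true for cancer.

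Reading 20-30% as the prevalence of each condition separately would, for cancer, conflict with section 1.8.

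Finally, section 2.1.1 treats IL-8 as complementary to neurotensin and not standalone, so its shortfall is minor.

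**Conclusion.** The point holds as a mismatch between the sizing and the primary analyses. It is not an arithmetic error: 400 and 553 are correct for the inputs used. The width of 0.1 belongs, approximately, to a pooled group that is not a planned primary contrast (0.089 to 0.105 at n = 500), and it is not delivered for cancer unless the cancer yield is far above the one figure the protocol gives. At 4% the width is about 0.22 (0.17 to 0.22 across methods); at an assumed 10% it is about 0.145 (0.11 to 0.145).

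Adenoma versus normal is roughly on target at 0.095 to 0.116. That rests on an AUC of 0.85, for which there is no adenoma pilot figure, and on cancers being about 4%. All figures treat every participant without cancer or adenoma as group C; fewer controls would barely change the cancer result.

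It may be tempting to conclude that 500 is the wrong number, or that a pooled primary analysis must be added to match section 3.5. Neither follows. The precision statement is what is wrong, and a new primary contrast would leave cancer precision unchanged.

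**What to change.** Keep n = 500 and the two existing primary contrasts. In section 3.5:

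- State the expected numbers of cancers and adenomas, with the cancer yield as an explicit assumption and a range.
- Give the expected 95% CI width for each contrast over that range. On the assumptions above: A versus C, about 0.22 at 20 cancers to about 0.145 at 50; B versus C, about 0.095 to 0.116 with 80 to 130 adenomas. Note that the AUC for adenoma is assumed, and name the variance formula.
- Add a supplementary line for IL-8 at AUC 0.81 (pooled width 0.096 to 0.113 at n = 500).
- Say that the 0.1 width holds only approximately, for the pooled group, and not for cancer. Describe the cancer AUC as an estimate at the wider precision.

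Do not add a pooled primary analysis. The cost is a revised paragraph and a less favourable stated precision for cancer. No extra patients or samples are needed.

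### The target of 500 meets the protocol's own precision goal only if adenoma/cancer prevalence is at least about 22.6%, and section 3.5 does not say so

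*Protocol*

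**What the plan says.** Protocol section 3.5 gives the only quantitative basis for the sample size. The planning value is set by "Assuming that the AUC of the new test is commensurate with the pilot study (AUC=0.85"), the precision goal is a 95% "confidence interval of size 0.1", and the model is stated as "We assume that the ROC curve follows a binormal distribution". The share of cases is given as a range: "the prevalence of adenoma/cancer is between 20-30% in the study participants". The result is "We obtain that we require between 400 (30% prevalence) and 553 (20% prevalence) participants", and the next sentence is "We therefore target an enrollment of 500 patients".

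Section 1.5 repeats 500 as the number to be analysed. Section 3.1 defines three groups (cancer, adenoma, normal colonoscopy) and two primary analyses: cancer against normal, and adenoma against normal.

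**The concern.** The target is presented as the consequence of a calculation whose upper requirement it does not meet: 553 − 500 = 53 participants, or 9.6% of 553. No sentence says that a wider interval is accepted at low prevalence, or that a prevalence inside the range was taken as the planning value. A reader of section 3.5 could therefore believe that 500 secures a width of 0.1 wherever prevalence falls between 20% and 30%.

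What is at stake is the accuracy of the stated precision. The AUC is part of the primary endpoint (section 3.3), and the interval width is the only property of the design that the sample size is said to guarantee.

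**Working it through.** **Inputs.** From section 3.5: AUC 0.85; 95% two-sided, so z = 1.96; full width 0.1, so half-width 0.05; binormal ROC; prevalence p from 20% to 30%; target N = 500. The variance formula is not named in the protocol. I used the Obuchowski binormal approximation, with R = non-cases per case = (1 − p)/p:

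- a = 1.414 × probit(0.85) = 1.414 × 1.0364 = 1.4655, so a² = 2.1477
- V = 0.0099 × exp(−a²/2) × [(5a² + 8) + (a² + 8)/R] = 0.0033827 × [18.739 + 10.148/R]
- required cases = 1.96² × V / 0.05²; required N = required cases / p

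**Reproducing the protocol's figures**

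| p | R | V | Cases | Required N | Protocol |
|---|---|---|---|---|---|
| 20% | 4.00 | 0.07197 | 110.6 | 552.9 | 553 |
| 25% | 3.00 | 0.07483 | 115.0 | 459.9 | not given |
| 30% | 2.33 | 0.07810 | 120.0 | 400.0 | 400 |

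Strict rounding up gives 401 at 30%, which is immaterial. Reading 0.1 as the half-width gives 139 and 101. The Hanley-McNeil variance gives 484 and 338, and a binormal delta-method variance with equal spreads gives 332 and 253. None of these matches, so the goal is a full width of 0.1 and the formula above is very probably the one used.

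**Width at N = 500.** Width scales as 0.1 × √(required N / 500):

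- 20%: 0.1 × √(552.9/500) = 0.1052
- 25%: 0.1 × √(459.9/500) = 0.0959
- 30%: 0.1 × √(400.0/500) = 0.0894

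Setting required N equal to 500 and solving for p gives 22.55%, so in practice about 22.6%. The goal is met for roughly three quarters of the assumed range and missed from 20% to about 22.5%.

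**If fewer than 500 are analysable.** Enrolment and analysis targets are both 500, although haemolysed samples and withdrawals are excluded (section 3.2) and the neurotensin kits are costed for 488 samples (section 7). At 488 the width at 20% is 0.1 × √(552.9/488) = 0.1064, and the break-even prevalence becomes 23.2%.

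**What these widths describe.** The calculation pools adenoma and cancer and sets them against everyone else. Neither primary analysis in section 3.1 uses that contrast. For illustration, suppose 4% of 500 have cancer, which is 20 people. The 4% is the general colonoscopy pick-up rate in section 1.8, not a figure for this cohort. With 350 to 400 participants in the normal group (500 less 30% to 20% cases), R is 17.5 to 20, V is about 0.065, and the full width is 2 × 1.96 × √(0.065/20), about 0.22.

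**The case against.** The strongest reply is that nothing here is miscalculated. Both requirements are correct, and the sentence before the target openly shows 553 at 20%. Prevalence is unknown, and choosing a number inside the calculated range is a legitimate planning decision: 500 exceeds the 460 needed at the 25% midpoint. The worst excess is about 0.0026 on each side of the AUC, and no decision rule depends on the width. The AUC input is also less certain than the gap. It comes from a pilot with 13 colorectal cancer patients and 15 healthy controls (section 2.1.1). With the same formula at 20% prevalence, an AUC of 0.87 needs 499 and one of 0.83 needs 599.

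Most of this stands. A reader might infer that the sample-size arithmetic is wrong, that a width of 0.1 is promised at every prevalence and generally not delivered, or that 553 must be recruited. The documents do not support any of these. The arithmetic reproduces, the protocol never states that 500 secures 0.1 throughout the range, and the goal is met over most of it.

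What does not fall away is the inference itself. The target is introduced as following from the calculation, and the condition under which it does follow is left for the reader to work out. It is also fair to object that simply printing the pooled widths would suggest a precision that the primary analyses do not have; the fix has to deal with that.

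**Conclusion.** The point holds as a limited one. Section 3.5 calculates its two requirements correctly but draws a target from them that meets the stated goal only when the combined adenoma/cancer prevalence is at least about 22.6%. At 20% the full width is about 0.105 instead of 0.1, some 5% too wide.

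This rests on the protocol's own assumptions (AUC 0.85, binormal ROC, full width 0.1) and on 500 analysable participants. The variance formula is inferred from its match to 400 and 553; under Hanley-McNeil, which the protocol does not name, 484 would suffice at 20%.

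The widths apply only to pooled cases against all others. The figure of about 0.22 for cancer versus normal is an illustration that depends on the assumed 4% and on the same AUC. It is not a prediction for this cohort.

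**What to change.** Keep the target of 500 and replace the concluding step in section 3.5 with wording such as:

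> With 500 analysable participants, the 95% CI for the AUC of pooled adenoma/cancer cases versus all other participants has a full width of about 0.105 at 20%, 0.096 at 25% and 0.089 at 30% prevalence. A width of 0.1 is reached only from about 22.6% prevalence.

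Then add the expected width for each primary comparison in section 3.1 (cancer versus normal, adenoma versus normal), with the assumed number in each group. These intervals will be wider where the case group is smaller, and the assumed cancer share should be stated as an assumption. Without this addition, the pooled figures would mislead about both primary analyses.

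The cost is a few sentences and a short calculation. Enrolment, procedures and analyses do not change; the stated precision becomes slightly less favourable for the pooled contrast and clearly less favourable for cancer versus normal if cancers are as few as in the illustration.
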